## **1. Introduction**

Dental caries is the most common chronic disease in children, and is even four times as common as asthma in adolescents. According to the National Health and Nutrition Examination Survey (NAHNES) from 1999 – 2004, 27.9 percent of children ages 2 – 5 have caries in the primary dentition, and that number increases to 51.17 for ages 6 – 11. When the income level for these children’s families is 200 percent that of the Federal Poverty Level, 42 percent of children have caries, but when compared to those at 100 percent of the poverty level the caries rate reaches that of 54.3 percent of children, with 32.3 percent of children at this level of poverty having untreated decay. For these children, living with this untreated dental disease may lead to problems with food intake, daily sleep, difficulty in school, restriction of daily activities, and negative impact to their self-esteem. Primary prevention of caries in children is always preferable, but is not always possible. When primary prevention fails, effective secondary prevention using treatments that are safe, simple, low-cost, and acceptable to patients can be efficacious in preventing morbidity to these children, which is our ultimate goal.

## **2. Objectives**

The objectives of this clinical study are to evaluate:

- The effectiveness of treatment of cavitated caries in children by application of silver diamine fluoride (SDF) in comparison to conventional restorative treatments
- The perceptions of parents and patients to both treatment modalities and their levels of acceptability
- The opinions of dental providers in terms of ease of use and clinical time spent
- The relative cost-effectiveness of the two treatment approaches regarding both practitioner chair time and material-based cost

### **3. Review of Literature**

#### **3.1. Silver in Dentistry**

Silver has been used in medicine for hundreds, even thousands, of years. Some of the earliest reports of the use of silver compounds in dentistry to reduce the incidence of caries in the primary dentition date back to the 1840s. In the late 60's and early 70's research by many groups worldwide began regarding the use of silver diamine fluoride to prevent caries. In more recent years, clinicians have come to the realization that finding treatments especially for those children in disadvantaged communities, is of utmost importance on a worldwide level. Because of the great need and often the inaccessibility of standard dental care, discussions have arisen regarding Arresting Caries Treatment (ACT) as opposed to traditional restorative dental treatments, which typically would involve complete caries removal and replacement of missing tooth structure with a restoration. Silver diamine fluoride offers many proposed advantages as an ACT – 1. It offers control of pain and infection. 2. Its ease of use is great. 3. It is highly affordable. 4. There is minimal time involvement for its application. 5. It is a non-invasive option.

#### **3.2. Silver Diamine Fluoride Mechanism of Action**

The favored caries prevention agent today worldwide is fluoride, and professional topical fluoride applications, such as fluoride varnish are now-a-days the most commonly used strategy in the U.S. for primary and secondary prevention of carious lesions, even though this caries prevention use for varnishes is off-label in the U.S. This use has been endorsed by organized dentistry in the U.S., including the American Dental Association, the American Academy of Pediatric Dentistry, State preventive programs funded by the Centers for Disease Control and Prevention, etc. SDF is a type of professional topical fluoride which has been approved in the U.S. with an application similar to that of fluoride varnishes. In fact, Oregon now allows hygienists and expanded function dental assistants to apply SDF under general supervision just as with any other fluoride or antimicrobial agent. SDF incorporates both of the advantages of fluoride to reduce dental caries and promote remineralization, and also offers a quite potent germicidal effect. It has been reported that it not only strengthens the sound tooth structure, but also offers the ability to kill bacteria and arrest caries progression once a cavity has developed. Research has shown that SDF has the ability to

inhibit colonization of *Streptococcus mutans*, *Actinomyces naeslundii*, and *Enterococcus faecalis*. Being of utmost importance to the caries progression process, the direct effects on *S. mutans* have been noted for years, with literature dating back to 1976. It is important to note that not only does SDF have the ability to prevent biofilm formation, but it also has the ability to kill the bacteria present at time of placement.

In addition to directly inhibiting bacterial growth, SDF also can reduce against acid solubility and facilitate enamel remineralization via other mechanisms. Early researchers believed the silver-salt formation stimulated sclerotic or calcified dentin formation. For decades now, it continues to be shown that the fluoride and silver present in SDF interact together to form fluorapatite strengthening the tooth. It has also been shown that not only is the depth of penetration of SDF far greater than that of other fluoride containing materials, but the tooth retains two to three times more SDF than with other fluoride combinations. Furthermore, the amount of reparative dentin formation has shown great increase when used prior to dental materials that have silver added. The combination of all this information demonstrates why SDF has been shown to be such an effective desensitizer as well. In comparison to active carious lesions with no treatment, those which were arrested at 24 months via biannual SDF application showed more well aligned and highly organized crystallites. The underlying collagen fibers were protected from exposure, and there was also a rich zone of calcium and phosphate, suggesting that clinically there is a highly positive effect on dentin remineralization due to the SDF application.

### **3.3. Previous Research Involving Silver Diamine Fluoride**

Research over the past few decades regarding the effectiveness of SDF has been relatively consistent. In comparison to 5 percent sodium fluoride (NaF; used commonly in professionally applied fluoride varnishes), 38 percent SDF was found to be more effective in arresting active caries in the primary anterior teeth of preschool children at 30 month follow-up. Continued research showed that not only could SDF arrest active caries, but additionally it could reduce the incidence of caries in the primary teeth as well as the first permanent molars in school children. Most recently it has been shown that annual SDF application has a similar rate of effectiveness in

arresting caries comparable to that of sealant placement or biannual application of 5 percent NaF after 24 months.

### **3.4. Negative Aspects of Silver Diamine Fluoride**

In addition to the numerous apparent positive effects of SDF there are a minimal number of drawbacks, the most notable being the black stain it leaves on the carious dentin. While esthetically unpleasing to some, this black stain is not of any physical harm to the patient. In fact when compared to applications of sodium fluoride and no treatment, all treatments had teeth presenting at recall with blackened dentin. Recent studies have shown this black discoloration appears to be a non-issue, as the coloration of the teeth following treatment did not decrease patient satisfaction. However, additional research has still been aimed at reducing the black discoloration of the tooth by placing potassium iodide (KI) following SDF application or by completely placing an alternative agent, such as ammonium hexofluorosilicate ( $(\text{NH}_4)_2\text{SiF}_6$ ). Placing potassium iodide may eliminate the staining, but whether this reduces the effectiveness of the SDF is still in need of further evaluation, especially *in vivo*. Research on ammonium hexofluorosilicate, on the other hand, shows that it is not effective in reducing caries progression and is therefore not a viable replacement option to SDF.

The most common concern with any product used intraorally is its compatibility with intraoral soft-tissues. Recent research has confirmed that tissue ulcerations and argyria were not present following treatment with SDF. Only transient mild erythema of the gingiva near the SDF-treated tooth and a metallic taste in the patients' mouths were noted in some patients, supporting that the use of silver diamine fluoride is quite safe.

### **3.5. Silver Diamine Fluoride Variations in Application**

While much of the previously presented research suggests that there are potential positive effects of SDF, there are still many potential variations in regimens for application. Many would assume that for effective arrest of caries, it would be important for carious debris to be removed reducing the bacterial load. However, it has been shown that caries removal did not offer any significant beneficial effect in terms of arresting carious lesions and only showed a reduction in the number

of arrested lesions that turned black in the NaF group, as 100 percent of the lesions in the SDF group presented with a black coloration regardless of caries removal. For this reason, it has been suggested that caries removal would be unnecessary, which would make the procedure more simple and could increase the potential for patient acceptability which is important because it is one of the advantages of this product.

Many studies have shown a variation in number of applications and concentrations, leading to the research question of determining an exact regimen. In terms of concentration, when observed at 6 months, it was noted that a single application of 38 percent SDF could arrest caries in comparison to 12 percent SDF, which could not. Regarding the optimal number of applications, it was shown that an annual topical application of 38 percent SDF would arrest 37 percent of caries at 12 months and up to 79.2 percent of caries at 24 months, while biannual applications resulted in 53 percent arrested caries at 12 months and 90.7 percent arrested caries at 24 months.

Due to the potentially highly positive caries arrest effects of SDF, research has been conducted in an attempt to prevent washing away of the product when placed on the tooth surface. It has been postulated that if the treated surface was to turn instantaneously black, this would indicate that the process had been accelerated and was in turn more effective. Studies have shown that applications of 10% stannous fluoride or tannic acid were not shown to have an additional benefit in arresting caries although they may have appeared to accelerate the process of SDF uptake by the tooth surface.

### **3.6. Current Research**

According to Rosenblatt et al., the advantages of SDF are numerous. While it can control the infection, it is also easy to use, highly affordable, involves minimal chair time, and is quite non-invasive. They also concluded there is no [published] research that addresses all of these topics. SDF was approved in the United States in July 2014 and currently there have been no clinical trials in the United States testing the application of SDF to arrest caries in children. Also, there seem to be no studies that address the failure rates of SDF in comparison to conventional one and two-surface restorations for the treatment of dentin caries. The researchers' aims in this study will be

to address affordability, ease of use, and both patient/parent and provider acceptance, in addition to clinical success rates when compared to conventional restorations.

## **4. Materials and Methods**

### **4.1. Purpose**

To determine the effectiveness of the application of silver diamine fluoride (SDF) in comparison to conventional restorative treatments in International Caries Detection and Assessment System criteria (ICDAS) 5 and 6, one and two surface carious lesions in primary molars which will be assessed based on major and minor failure criteria when followed for one year. Additionally, parents'/children's and providers' perceptions will be assessed as well as the cost of both regimens, to include both chair time spent and materials' costs.

### **4.2. General Outline**

Children, 2-10 years of age will be invited to participate. The original study site is Mott Children's Health Center (MCHC) in Genesee County, Michigan. Following a slow recruitment period, the University of Michigan School of Dentistry (UMSOD) Children's Clinic was added as a second study site. Given the current data in the literature, the combined failure rate for conventional restorative techniques (e.g. compomers) is approximately 29% at one year follow-up, while application of silver diamine fluoride has a failure rate of 63% at one year follow-up, with increased success over time. Although the failure rate of SDF at one-year follow-up seems alarming, as indicated by Zhi, *et al.* it may be possible to increase the success rate with additional applications providing success rates up to 90.1% at 24 months. Using these data,  $\alpha$ -value of 0.05 and a Power set at 80%, the resulting sample size would be 68 (34 per group) as calculated using the software, nQuery (Appendix 1). To account for 30% attrition, the final number needed for the initial study will be 98 (92 for 25% attrition, 86 for 20% attrition). Subjects will be contacted by phone regularly and invited to two intermediate clinic visits (plus a final study visit) to reduce attrition (Table 1). Given a review of the current literature of the few Randomized Controlled Clinical Trials involving SDF worldwide, the majority of this research has been completed with pre-school aged children. Almost all research discusses arresting or prevention of caries in the

primary dentition, as well as prevention of caries on first permanent molars. Due to the strength of the current research, this study will be focused on the primary dentition of children in the U.S. These children and their parents will be approached when presenting for examination/recall/or treatment at Mott Children's Health Center, Flint, MI, or the University of Michigan School of Dentistry Children's Clinic, Ann Arbor, MI. Interested families with children that qualify following screening examination will be provided with an *Informed Consent/Assent* (Appendix 3) and an *Enrollment Information Form* (Appendix 4).

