Children who are enrolled to participate in the study will receive a full mouth caries examination using the ICDAS criteria (Examiners will be trained and calibrated in the ICDAS criteria prior to study initiation.), and will be randomly divided into two groups:

1. **Conventional management of caries group:** This group will receive traditional restorative care for one tooth with a one or two surface lesion – including composite, amalgam, or glass-ionomer restorations according to the current AAPD treatment guidelines.
2. **SDF management of caries group:** This group will receive applications of SDF applied to their carious lesion, in lieu of restoration placement, with the goal of “arresting caries”.

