### **5.2. SDF management of caries**

- The selected tooth with notable decay into dentin will be isolated with cotton rolls.
- No caries removal will be performed, except for food or other obvious debris.
- Tooth will be dried with gauze and SDF solution will be placed on the carious dentin until it is saturated.
- Excess SDF will be blotted dry with a cotton pellet.
- A second application of SDF solution will then be placed to ensure that the entire carious surface is wetted, and excess will again be blotted with a cotton pellet.
- Following the second application of SDF, the area will be isolated for 3 minutes to allow for ample drying before allowing contact with saliva and soft tissues
- Should the SDF come in contact with any soft tissues, soft tissue should immediately be wiped with a saline wipe
- Following completion of the SDF intervention visit, the provider will complete the CRF 03 *Intervention Visit: Silver Diamine Fluoride* CRF (Appendix 10, CRF 03).
- A second application of SDF will be applied at 6 month recall, following the same protocol as noted above (Due to the potential for increased caries arrest rate with a 6 month application).
- Any new carious lesions that develop after the initial treatment will be recorded, and treated using conventional treatment methods and will not be included in the study.
- Following the completion of this study, teeth in the SDF group will be treated according to AAPD guidelines or observed for exfoliation. The parent of an SDF treated child can elect a restoration following AAPD guidelines at the 12 month visit.

Both groups will receive the following, according the standard procedures at the MCHC/UMSOD:

- Oral Health Instruction (OHI) and diet instruction
- Tooth brushing/dentifrice use at home
- Fissure sealants for permanent teeth will be placed if deemed necessary.
- Traditional preventative care at recalls based on AAPD guidelines (Regular recall exams, prophylaxis, scaling, flossing, and fluoride varnish at 6 month recalls will be provided for both treatment arms. Special care will be taken to not apply fluoride varnish directly to the carious lesion which is being treated with SDF.)

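### Section 4.2's 80% power depends on an SDF failure rate for annual application, while this trial reapplies SDF at 6 months; at the same source's biannual rate, power at 34 per group would be 33%

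*Combined protocol and SAP*

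**What the plan says.** **Sizing (Section 4.2).** Two one-year failure rates are used. For the conventional arm, "the combined failure rate for conventional restorative techniques (e.g. compomers) is approximately 29% at one year follow-up". For the SDF arm, "application of silver diamine fluoride has a failure rate of 63% at one year follow-up", citing reference 28. With alpha 0.05 and 80% power these give 34 per group, raised to 98 enrolled for 30% attrition. The following sentence, under the same reference, adds that "it may be possible to increase the success rate with additional applications providing success rates up to 90.1% at 24 months". The calculation does not use this.

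**Background (Section 3.5).** Reference 28 is reported by regimen: "an annual topical application of 38 percent SDF would arrest 37 percent of caries at 12 months", whereas "biannual applications resulted in 53 percent arrested caries at 12 months and 90.7 percent arrested caries at 24 months".

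**Treatment (Section 5.2).** The SDF arm is treated at baseline and again later: "A second application of SDF will be applied at 6 month recall". The reason given, again from reference 28, is "Due to the potential for increased caries arrest rate with a 6 month application".

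**Failure (Sections 6 and 7.2).** Table 2 gives the trial its own minor and major failure criteria. Section 6 withdraws a child at either kind of failure and counts the tooth as failed.

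**Analysis (Section 10).** The 80% is repeated as the power of the study, and major failure is named as the primary outcome.

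**The concern.** The protocol adds a 6-month application because it expects more arrest, but it sizes the trial on the arrest rate of the regimen without that application. Section 4.2 does not say that its 63% is the annual figure.

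The direction matters. This is a test for a difference in which SDF is assumed to fail more often. A high SDF failure rate therefore widens the assumed gap and reduces the sample needed, so 63% is not a cautious choice as far as power is concerned. If reapplication works as hoped, the gap narrows and power falls.

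What is at stake is interpretation. A non-significant comparison reported beside a flat 80% could be taken as showing that SDF is as effective as restoration, when the trial may have had little chance of detecting a difference of the size its own background section reports.

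**Working it through.** **Inputs.** Conventional failure p1 = 0.29 and SDF failure p2 = 0.63 (Section 4.2). Alternative p2 = 1 − 0.53 = 0.47 (Section 3.5, biannual); the annual figure, 1 − 0.37 = 0.63, confirms the origin of the 63%. Allocation is 1:1 (Section 4.4). Evaluable n is 34 per group; full enrolment is 98/2 = 49 per group. Alpha is 0.05. Sidedness is not stated, so two-sided is assumed.

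**Formulas** (pooled variance, no continuity correction), with d = p2 − p1, m = (p1 + p2)/2, A = √[2m(1 − m)] and B = √[p1(1 − p1) + p2(1 − p2)]:

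- n per group = [1.960·A + 0.842·B]² / d²
- power = Φ[(d√n − 1.960·A)/B]

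**Reproducing the plan (0.29 vs 0.63).** d = 0.34, m = 0.46, A = √0.4968 = 0.7048, B = √0.4390 = 0.6626.

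- n = (1.3815 + 0.5576)²/0.1156 = 32.5, so 33 per group against 34 stated. A one-sided test would give 26 and a two-sided test with continuity correction 39, so two-sided without correction fits best.
- Power at 34: (0.34 × 5.831 − 1.3815)/0.6626 = 0.907, Φ = 82%.
- Power at 49: (0.34 × 7 − 1.3815)/0.6626 = 1.507, Φ = 93%.
- Attrition: 68/0.70 = 97.1, so 98 in two equal groups. This matches.

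The arithmetic of the plan is sound. Only the input is in question.

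**Same calculation at the biannual figure (0.29 vs 0.47).** d = 0.18, m = 0.38, A = √0.4712 = 0.6864, B = √0.4550 = 0.6745.

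- Power at 34: (0.18 × 5.831 − 1.3454)/0.6745 = −0.439, Φ = 33%.
- Power at 49: (0.18 × 7 − 1.3454)/0.6745 = −0.127, Φ = 45%.

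| SDF failure | 34 per group | 49 per group |
|---|---|---|
| 63% (annual) | 82% | 93% |
| 47% (biannual) | 33% | 45% |

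**Check by exact enumeration of the uncorrected chi-square test.** At 63%: 81% and 94%. At 47%: 35% and 45%. The approximation is adequate.

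**Detectable difference.** With conventional failure at 29%, 80% power is reached at SDF failure of 62.3% with 34 per group and 56.7% with 49. The differences are 33.3 and 27.7 points, about 33 and 28.

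**Width of the interval.** If 29% and 47% were observed at 34 per group, the odds ratio would be (0.47 × 0.71)/(0.53 × 0.29) = 2.17, with a 95% Wald interval on the log scale of 0.80 to 5.91. Such a result is non-significant but far from showing equal effectiveness.

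**Secondary: the 29%.** It is also an assumption. Section 4.2 gives compomers as its example, while Section 4.3 describes the conventional arm as "including composite, amalgam, or glass-ionomer restorations according to the current AAPD treatment guidelines". As an illustration only, conventional failure of 20% or 35% would make power at 63% SDF failure 97% or 64% at 34 per group.

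**The case against.** The strongest reply is that 47% may be the less relevant figure for this trial. Section 6 withdraws children at failure and counts the tooth as failed, and Table 2 lists soft dentin under minor failure. If softness at 3 or 6 months is enough, a lesion that would harden only after the second application has already failed. On that reading 47% is closer to a floor, and the trial's rate may be near or above 63%, where power is 82% or more at 34 per group with 29% conventional failure. This stands. A reader might infer from the table that the trial is underpowered, or that 47% is the rate it should have used. The documents support neither.

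Nor do they settle the rule itself. Every study lesion is soft at entry (Section 4.3). A provider can withdraw a child whose treatment is failing (Section 4.4), but Section 6 says that the child will be withdrawn. Table 1 puts reapplication and failure assessment at the same 6-month visit. Whether unchanged softness alone is failure is not clear.

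Three smaller points also stand in part. Section 4.2 does mention additional applications in its next sentence, so the idea is disclosed, although the 63% itself is not identified as annual. Compomers are only an example, so the 29% may cover other materials; a reader might conclude that it comes from the wrong materials, but this cannot be shown without the source. The nQuery output in Appendix 1 is not in the text available, so the lack of a sensitivity range is confirmed only for the body of the protocol.

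**Conclusion.** The concern holds as a point about a conditional power statement. The 63% belongs to annual application, the trial reapplies at 6 months, and the same reference gives 47% for biannual application. Across those two documented rates, power for combined failure runs from 82% down to 33% at 34 per group, and from 93% down to 45% at 49. Full retention therefore does not remove the dependence.

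These figures assume 29% conventional failure, a two-sided 0.05 test and combined failure as the outcome. They do not describe power for major failure, the primary outcome in Section 10; that mismatch is a separate matter and adds no weight here. The conclusion is that the 80% is not supported for this regimen as written, not that the true power is low. The point is worth correcting because the remedy is only text and it governs how a null result will be read.

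**What to change.** Make no change to enrolment. In Section 4.2 keep the 80% derivation of 68, and add after it:

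> The 63% is the 12-month non-arrest figure for annual application; for biannual application the same source gives 47%. This trial reapplies SDF at 6 months and uses its own failure criteria, so its rate is uncertain. With 29% conventional failure (an assumption), power for combined failure at 34 (49) per group is 82% (93%) at 63% SDF failure and 33% (45%) at 47%; the difference detectable with 80% power is about 33 (28) points.

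Confirm the sidedness against the nQuery output first; if it was not two-sided, recompute these figures.

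In Section 10 replace the opening statement on power with:

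> The 80% refers to combined failure under 63% versus 29%. A non-significant result will be read through the 95% confidence interval and not as evidence of equal effectiveness.

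Separately, the passages on soft dentin, failure and withdrawal at 3 and 6 months, and the 6-month reapplication (Sections 4.3, 4.4, 6 with Table 1, and 7.2 with Table 2) must be reconciled by the investigators. The sample-size text should not settle that rule.

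The cost is five sentences, with no change to visits, data collection or tests. The downside is that the stated power becomes less favourable.
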